After the baseline assessment, infants in the START-Play group will begin the intervention *with therapists from the START-Play project trained specifically in the START-Play intervention*, and the infants in the control group will continue with their regular services *with their community service provider*. All infants will receive the same assessments, as well as survey instruments to the families to determine the level of other services received by the infant. All infants will have regular intervention sessions videotaped at least once for quantification of procedures and to assure the fidelity of the intervention being provided across children.

The control intervention is the usual Early Intervention services provided to infants and mandated by public law, which consists of general developmental education and advice and in some cases low frequency therapy. Infants randomized to the intervention group will receive home visits twice weekly for the START-Play physical therapy intervention for three months. *The daily intervention will be provided by the caregiver, based on suggestions from the twice weekly visits of the START-Play therapist*. The START-Play Intervention is designed to advance sitting and reaching, and secondarily improve exploration, manipulation and problem-solving skills. *The START-Play therapy visits will be provided by either the primary investigator or by a consultant therapist (from Children’s Hospital trained and supervised by the PI*. See appendix B in full proposal for examples of START-Play intervention activities.

4. Instruments

1) Primary Measures for Sitting and Reaching

These variables quantify the initial functional delays in these skills and changes during the Intervention and Follow-up periods. *Data will be collected using video by a START-Play assessment therapist and the post doctoral fellow on the START-Play grant (to be hired)*. *Data reduction and coding will take place at various sites, with each site having a focus (Duquesne for kinematics, Delaware for reaching, VCU for problem solving, UW for Bayley and GMFM, UNL for fidelity and overall statistical analysis and data management*.

- GMFM sitting section

The Gross Motor Function Measure (GMFM, Russell et al 1993) is the international standard outcome assessment tool for quantifying change in the gross motor abilities of children with neuromotor disorders (inter-rater reliability, $r=.97$, Russell et al 2000).

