- c. problem-solving Variable: IGDI problem-solving score
- d. global development Variable: Bayley III score

Hypothesis 2: Compared to the BAU group, the START-Play group will show greater sustained improvements from pre-intervention to one year since start of intervention (long-term effect) in:

- a. sitting Variable: Gross Motor Function Measure (GMFM) sitting scores
- b. reaching Variable: Number of toy contacts
- c. problem-solving Variable: IGDI problem-solving score
- d. global development Variable: Bayley III score

Hypothesis 3 (Mediation): Improvements in global development will be (at least) partially mediated by improvements in problem-solving as a function of the intervention at the end of the project (long-term proximal effect).

Variables: GMFM scores, toy contacts, IGDI problem-solving and Bayley III scores.

SECONDARY HYPOTHESES

Analysis of moderators

1. *Hypothesis:* Severity of motor impairment will have a significant influence on overall change in IGDI problem-solving, and motor scores, as well as Bayley III scores. Variable: Severity score (see Table 1)

2. *Hypothesis:* Factors external to the child (socialization opportunities [Modified Parent Child Interaction-Dyadic Mini Code scores (Censullo, 1991) (PCI-DMC)], and home environment (HOME Inventory [Bradley, 1993] & SES), will have a moderate effect on change in GMFM, problem-solving, and Bayley III scores.

Further analysis of motor variables

3. *Hypothesis:* The START-Play group will show posture control measures that are closer to normative values than the BAU group from pre to post intervention. This hypothesis tests additional variables quantifying sitting to supplement Primary Hypothesis 1. Variables: Kinematic measures taken from video analysis.

4. *Hypothesis:* Compared to the BAU group, the START-Play Intervention group will show greater improvements in duration of toy contact and object manipulation from pre to post intervention. This hypothesis tests additional variables quantifying reaching to supplement the

Primary Hypothesis 2. Variables: Unilateral and bilateral contact number and duration, and type of contact (i.e. hand open or closed; palmar or dorsal hand surface, manipulation variables).

iii. Research Design

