We propose a 3-month randomized trial with repeated measures design plus a nine-month follow-up. The design is longitudinal to best capture changes over time within both the BAU group and the START-Play group, and to distinguish advances in skill due to the specific intervention vs. general development under the usual model. Recruitment of study participants will be continuous throughout the project’s recruitment period, and assignment to condition will occur at the individual child level. It will not be possible to have a control group without intervention because all recruited children will be delayed enough to have mandated early intervention services. The experimental group will receive the START-Play intervention as well as their regular Part C services. Randomization will be stratified by the severity of neuromotor disorder (mild, moderate and severe). This stratification will help to ensure that the intervention groups are balanced. Randomization will be created using a random number generator using blocks of size 4 or 6, and arranged in sealed envelopes by our biostatistician, separately for each site. Numbered group assignment will be dated and faxed to the PI to verify the process.

A scale created in a previous US Dept. of Education NIDRR-funded study of infants with CP helps ensure equal distribution of children with varying severity of neuromotor dysfunction, and has been adapted for this study. The scale is summarized below:

Table 1. Method to Determine Severity of Disorder

Score Received on the Measure	Measures			
	Distribution	Active Movement	MACS	GMFCS
1	1 side	High	1-2	1-2
2	primarily legs	Moderate	3	3
3	all 4 extremities	Low	4	4

Scores from each column are totaled for a final score: 9-12, Severe; 6-8, Moderate; 4-5, Mild.

- Distribution refers to the areas of the body affected by neuromotor dysfunction.
- MACS: Manual Abilities Classification Scale (Hidecker et al, 2009) describes use of the hands and arms
- GMFCS: The Gross Motor Function Classification System (Palisano et al, 1997) classifies a child’s motor involvement on the basis of functional gross motor abilities.

The assessment schedule covers entry month (between 7-16 months of age) and the following 12 months (between 19-28 months of age). Assessments are at Baseline, Intervention (Rx) and Follow-up. Table 2. Assessment Schedule

Assessment number	1	2	3	4	5	6
Timetable (months after study entry)	0	1	2	3	6	12

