	Business-as-usual*	START-Play	Difference
Frequency	Once weekly to once monthly	Twice weekly	Increased frequency of interaction
Intervention Model	Transdisciplinary or interdisciplinary- may be teacher, PT, OT or Speech	Short term focus with expert in motor (physical therapist) in partnership with parent for activities below (Appendix C)	Increased focus for caregiver on understanding motor and linkage to problem-solving
Content of Session	Directed to Parent: (25%) 
 • Parent Training 25% Directed to Child: (55%) 
 • Task Guidance w/ PT 25% • Postural Control & Strengthen w/ PT 20% • Tolerate Positions 10% • Equipment/Stretch w/ PT 10% 	Directed to Parent: (35%) 
 • Analysis with parent & setup 20% • Parent-led activity 15% Directed to Child: (40%) 
 • Child-led activity with sitting /reaching 25% • Expand child-led activity - variability 15% Readiness to learn related: (25%) 
 • Link motor acts to problem-solving and cognition 25% 	Parent/caregiver taught all aspects, not just tasks, but also the “why” behind the action, connections to previous and later skills, problem-solving links, cognitive outcome expected for each action

	Readiness to learn related: (10%) • Cognitive - < 10%		
Example Content	
 1. Practice sitting balance reactions on a ball (isolated motor task) 2. Therapist provides supportive seat to constrain trunk, and suggests presenting toys on tray in front of infant and modeling use of toy 	
 1. Select activity for motor based problem solving – finding hidden toy. Child encouraged to shift weight, re-orient to look behind/under/in containers, thus building sitting balance in the service of spatial understanding 2. Dynamic low support sitting allows child to re-orient and gain spatial understanding; multiple options for variable sitting support depending on problem-solving task. 	
 1. Cognitive construct is selected first and is primary; movements are built around the cognitive construct 2. Parents taught that chair is passive and not variable. Multiple options, with minimal support needed, allow exploration and link motor to problem solving

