over time between motor skill and cognitive skill. Testing for mediation will take place by 1.) showing that global development change is influenced by change in sitting and reaching and 2.) change in reaching and sitting are linked to problem solving, 3.) change in problem solving is linked to change in global development and 4.) the effect of change in sitting and reaching on global development is at least partially explained by change in problem solving.

Other factors which may be moderators of the final outcomes are 1) severity of neuromotor disorder, 2) health status, 3) age at entry, 4) cognition at entry. Factors external to the child which may moderate outcomes are: 1) Socioeconomic status, 2) compliance or attendance to the program visits, 3) the home environment (HOME), 4) overall amount of service provided to the child, and 5) fidelity of intervention implementation. We expect that these moderating variables will not be different between groups because of our randomization process, however tests for initial differences between groups will verify this. In addition, testing for moderation will take place after the primary research questions are addressed. Variables will be tested individually first and later in combination to account for increases in explained variability.

ix. Data Analysis: Evaluation of Specific Aims and Hypotheses

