Evaluation of Secondary Hypotheses 1 & 2: Improvements in sitting, reaching, problem-solving and global development will be moderated by (1) internal variables: the severity of neuromotor disorder, health status, entry age, cognitive status at entry; and (2) external variables:

Figure 2. Mediated Effects Model for Hyp. 3 & 4

Note: RX = intervention phase; LT = follow-up phase; START-Play = assignment to condition; A,C = direct effects of the intervention on proximal & distal outcomes, B₁ & B₂ = effect of mediator(s) on other outcomes

socioeconomic status, compliance/attendance to home visits, the home environment (HOME), and overall amount of service to the family and child. Evaluation of these variables as moderators of the effect of the intervention on change in primary outcomes (sitting, reaching, problem solving and global development) will be done by modifying the LMM model equation used in evaluation primary hypothesis 2. Two three-way interaction terms, $TRT_{0i}RX_{it}MOD_{1i}$ and $TRT_{0i}LT_{it}MOD_{1i}$, where MOD_{1i} represents an individual moderator, will be added to the model to capture the intervention by time by moderator interaction. The simple effect of the moderator, MOD_{1i} , will be included as well as relevant 2-way interactions. All continuous variables will be mean-centered prior to forming cross-product interaction terms, and all categorical variables will be dummy coded prior to forming interaction terms. Each potential moderator will first be entered individually, and later in combination, with each primary outcome tested separately.

Evaluation of Secondary Hypothesis 3: Relative to infants in the BAU group, infants in the intervention group will show greater improvements in sitting control both post-intervention and at long-term follow-up. Evaluation of this secondary hypothesis will utilize the same LMM framework presented for evaluating primary hypotheses 1 and 2, with the exception that the outcome measures will be trunk forward bending, angular displacement, and velocity of trunk.

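### The planned test of Secondary Hypothesis 2 leaves out PCI-DMC and treats post-randomisation dose variables as moderators that randomisation will balance

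*SAP*

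**What the plan says.** SAP section ii (and Protocol section 1) names three external factors in Secondary Hypothesis 2: "socialization opportunities [Modified Parent Child Interaction-Dyadic Mini Code scores" (PCI-DMC), HOME and SES. SAP section v lists PCI-DMC first among the environmental measures.

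The evaluation of Secondary Hypotheses 1 and 2 in SAP section ix lists different external moderators: "socioeconomic status, compliance/attendance to home visits, the home environment (HOME), and overall amount of service to the family and child". SAP section viii gives the same four and adds fidelity of implementation. Neither list contains PCI-DMC.

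On balance, SAP section viii states "We expect that these moderating variables will not be different between groups because of our randomization process", and continues: "however tests for initial differences between groups will verify this".

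On exposure to visits:
- Protocol section 3: "Infants randomized to the intervention group will receive home visits twice weekly for the START-Play physical therapy intervention for three months".
- SAP section iii: "The experimental group will receive the START-Play intervention as well as their regular Part C services".
- SAP Table 4 gives the business-as-usual (BAU) frequency as "Once weekly to once monthly" and describes the contrast as "Increased frequency of interaction".
- SAP section v records attendance as a count of completed visits, and section vi logs home visits in both groups.

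SAP section ix adds two three-way terms for each moderator (treatment by intervention-phase time, and treatment by follow-up time), with continuous moderators mean-centred.

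**The concern.** There are two separate problems.

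First, the test does not match the hypothesis. One of the three named factors has no planned analysis, and two variables that the hypothesis does not name are tested in its place.

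Second, randomisation balances characteristics that exist before treatment starts. Attendance, amount of service and fidelity come into being afterwards, partly because of the assigned arm. A test for initial differences has nothing to examine for them. If they are entered as ordinary moderators, a significant three-way term could be reported as showing that the randomised effect depends on dose. In fact it would rest on comparisons among families who kept more or fewer visits for their own reasons.

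A related gap concerns HOME and PCI-DMC. START-Play works through the parent, so a value taken after it begins may already reflect treatment. The SAP does not say which time point supplies the moderator.

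**Working it through.** No stated power or sample-size figure bears on this point, so there is none to reproduce. The check compares the texts and then uses the plan's own visit frequencies.

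**Step 1. Hypothesis against test**

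| Factor | Secondary Hyp. 2 (SAP ii) | SAP viii list | SAP ix test | Arises |
|---|---|---|---|---|
| PCI-DMC | yes | no | no | before treatment, can change later |
| HOME | yes | yes | yes | before treatment, can change later |
| SES | yes | yes | yes | before treatment |
| Attendance | no | yes | yes | after randomisation |
| Amount of service | no | yes | yes | after randomisation |
| Fidelity | no | yes | no | after randomisation |

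A figure caption interrupts the list in section ix, but section viii independently omits PCI-DMC. Lost text is therefore an unlikely explanation.

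**Step 2. Planned visits by arm**

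Take three months as 13 weeks.
- BAU: monthly gives about 3 visits and weekly gives 13, so 3-13.
- START-Play: 2 × 13 = 26 study visits plus usual services, so 26 + 3 = 29 to 26 + 13 = 39.
- With 12 weeks: 3-12 against 24 + 3 = 27 to 24 + 12 = 36.

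The ranges meet only if a START-Play child with the fewest usual visits keeps 13 − 3 = 10 or fewer of the 26 study visits (10/26 = 38%). If attendance in that arm counted study visits alone, they would meet at 13/26 = 50%.

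**Step 3. What the three-way term measures**

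Write each child's change over the intervention phase as b0 + b1·T + b2·M + b3·T·M, with T the arm and M the visit count.
- The dose slope is b2 in BAU and b2 + b3 in START-Play, so b3 is the difference between two within-arm slopes. Neither slope is randomised.
- Replacing M by M − c leaves b3 unchanged. The lower-order treatment term becomes b1 + b3·c, the arm difference at c visits. As an illustration, at full attendance with usual visits averaging 8 (the midpoint of 3-13), the pooled mean is (8 + 34)/2 = 21. This lies between 13 and 29, so the term is an extrapolation from both arms.

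**Step 4. Sensitivity to the shape of the dose relation (assumed, not from the documents)**

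Simulations used 70 per arm, usual visits uniform on 3-13 and residual SD 1. With no dose effect, b3 was significant at 0.05 in 4.8% to 5.5% of trials (attendance 70% to 100%). In a similar set-up with 76 per arm, no dose effect or a linear dose effect common to both arms gave 5.0% to 5.7%.

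The next run used one concave curve common to both arms and no arm effect: mean change 2.4·(1 − e^(−M/8))/(1 − e^(−30/8)). It rises from 0.77 at 3 visits to 1.97 at 13, but only from 2.39 at 29 to 2.44 at 39. At 80% and 90% attendance, b3 was significant in about 57% to 58% of trials. This curve is deliberately steep at low doses. It shows the mechanism and does not estimate the risk in this trial.

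**The case against.** The best defence is that moderation is tested after the primary questions, so no primary estimate, sample size or error rate is touched. That stands, and it limits the importance of the point.

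Three stronger readings are tempting, and the documents do not support them.
- A reader might infer that any finding of moderation by dose would be an artefact of the arms' different visit counts. It need not be. As Step 3 shows, a gap in mean visits does not by itself create a three-way effect, and with no dose effect or a shared linear one the test keeps close to its nominal level.
- A reader might infer that the near-collinearity of arm and visits ruins the precision of the moderation test. The inflated standard error belongs to the lower-order treatment-by-time term, and the choice of centre does not alter the three-way term. Nor can one say that no child lies at the centring value: the SAP does not say that the mean is pooled, and lower attendance brings some children near it.
- A reader might infer that amount of service must differ by design as visits do. SAP section vi describes dosage as covering START-Play, early intervention and outpatient care, but has the Therapy Services Form count services outside START-Play and early intervention. Section v ties amount of therapy to that questionnaire, and section vii describes it more broadly. On the narrow reading the arms need not differ by design. Likewise, compliance read as the proportion of scheduled visits kept need not differ, although section v records a count. Either version is still measured after randomisation.

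On timing, the assessment schedule shows only the videos and three standardised tests, and the assessment manual is in an appendix not available here. The absence of HOME and PCI-DMC from that table does not show that they are not collected at month 0, nor is there text showing that they are.

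**Conclusion.** The point holds in two parts. PCI-DMC is named in Secondary Hypothesis 2 and measured, but has no planned moderator test. The SAP also extends a balance claim that is valid for baseline variables to attendance, amount of service and fidelity, where randomisation gives no such assurance and baseline tests cannot supply it.

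For visit counts the planned separation is 3-13 against 29-39 at full attendance. It rests on 13 weeks, the SAP's own frequencies and usual services continuing in both arms. With these variables the three-way term is a contrast of observational dose slopes. It is open to confounding and, because the ranges scarcely overlap, to non-linearity in dose. The treatment-by-time term in the same model should not be interpreted. A reader might go further and conclude that parent-child interaction will never be examined. The text shows only a mismatch between lists, which a correction would resolve.

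This is a correction that should be made to a secondary analysis; the primary comparisons do not depend on it.

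**What to change.** Amend SAP section viii and the evaluation of Secondary Hypotheses 1 and 2 in section ix:

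1. Add PCI-DMC to the moderator models.
2. Specify the baseline value (month 0, before the first START-Play visit) for HOME, PCI-DMC and any other moderator that can change, and state that these are collected then.
3. Limit the statement about balance, and the tests said to verify it, to baseline variables.
4. Define amount of service: all visits, or only services outside START-Play and early intervention. State whether attendance is a count or a proportion.
5. Take attendance, amount of service and fidelity out of the moderator tests of Secondary Hypothesis 2. Report them by arm, and relate dose to change within the START-Play arm only, labelled observational and exploratory.

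The cost is mainly wording. If HOME or PCI-DMC is not already planned at month 0, it would have to be added to that visit. The small downside is that dose-response becomes a non-randomised description, which is all that these data can support.
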